#### 7.6.3 Hematologic Toxicity

Hematological dose limiting toxicity is defined as:

- Grade 4 thrombocytopenia or neutropenia, not due to malignant infiltration.
- Grade 3 thrombocytopenia that persists for  $\geq$  7 days.
- Grade 3 thrombocytopenia requiring a platelet transfusion on two separate days, within a 7-day period.
- Grade 3 thrombocytopenia with clinically significant bleeding.
- Neutropenia or thrombocytopenia that causes a delay of  $>$  14 days between treatment cycles (e.g. platelets  $<$  100K or ANC  $<$  1000).
- NOTE: Grade 3 or 4 febrile neutropenia will not be considered a dose-limiting toxicity.

#### 7.6.4 Dose Modifications for Hematological Toxicity

If a patient experiences hematological dose-limiting toxicity as defined in Section 7.6.3, treatment will be held.

Counts should be checked every 3-4 days for thrombocytopenia and every other day for neutropenia during this time. If the toxicity resolves to meet eligibility parameters within 14 days of drug discontinuation, the patient may resume treatment at a reduced dose. The dose will be reduced by 25% so that patients receive 75% of the original administered dose. For subjects taking 800 mg twice daily (dispensed as 4, 200-mg tablets twice daily), dosage should be reduced to 600 mg, dispensed as 3, 200-mg tablets twice daily.

Doses reduced for toxicity will not be re-escalated, even if there is minimal or no toxicity with the reduced dose.

If toxicity does not resolve to meet eligibility parameters within 14 days of drug discontinuation, the patient must be removed from protocol therapy. If hematological dose-limiting toxicity recurs in a patient who has resumed treatment at the reduced dose, the patient must be removed from protocol therapy.

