### 7.6.2 Dose Modifications for Non-Hematological Toxicity

If a patient experiences non-hematological dose-limiting toxicity as defined in Section 7.6.1, treatment will be held. When the toxicity resolves to meet eligibility parameters or baseline within 14 days of drug discontinuation, the patient may resume treatment at a reduced dose as below.

Patients who experience dose-limiting toxicity should have their dose reduced by 25% so that patients receive 75% of the original administered dose. For subjects taking 800 mg twice daily (dispensed as 4, 200-mg tablets twice daily), dosage should be reduced to 600 mg, dispensed as 3, 200mg tablets twice daily.

Doses reduced for toxicity will not be re-escalated, even if there is minimal or no toxicity with the reduced dose.

If toxicity does not resolve to meet eligibility or baseline parameters within 14 days of drug discontinuation, the patient must be removed from protocol therapy. If dose-limiting toxicity recurs in a patient who has resumed treatment, the patient must be removed from protocol therapy.

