#### Adults

Dose level	Initial Dose: 8 capsules per day
Starting Dose	Four 200-mg capsules twice daily (1600 mg/day)
Dose Reduction (by 25%)	Three 200-mg capsules twice daily (1200 mg/day)

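### Sections 7.6.2 and 7.6.4 do not give one clear instruction for a first hematological dose-limiting toxicity in a patient already dose-reduced for a non-hematological one, and the reduction 7.6.4 offers is 0 mg

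*Combined protocol and SAP*

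**What the plan says.** Dose-limiting toxicities (DLTs) are handled in two parallel sections.

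- **Section 7.6.2 (non-hematological).** Treatment is held, and the patient may restart after recovery within 14 days. The restart dose is fixed: "Patients who experience dose-limiting toxicity should have their dose reduced by 25% so that patients receive 75% of the original administered dose". The closing rule is: "If dose-limiting toxicity recurs in a patient who has resumed treatment, the patient must be removed from protocol therapy". That sentence names no class of toxicity.
- **Section 7.6.4 (hematological).** The trigger is: "If a patient experiences hematological dose-limiting toxicity as defined in Section 7.6.3, treatment will be held". There is no exception for a patient whose dose has already been cut. Then: "If the toxicity resolves to meet eligibility parameters within 14 days of drug discontinuation, the patient may resume treatment at a reduced dose". The size of the cut is: "The dose will be reduced by 25% so that patients receive 75% of the original administered dose". The closing rule requires removal under this condition: "If hematological dose-limiting toxicity recurs in a patient who has resumed treatment at the reduced dose". This one does name the class.
- **Section 7.6.5, Table 3.** There is one reduced level per age group. For adults it is "Three 200-mg capsules twice daily (1200 mg/day"); for children it is 390 mg/m² per dose, capped at 1200 mg/day.

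Both 7.6.2 and 7.6.4 forbid re-escalation. Section 7.2 repeats the 75%-of-original rule and points to 7.6 for removal because of DLT.

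**The concern.** The two closing rules look like a matched pair, but one is limited by class and the other is not. The difference matters when the second DLT is hematological and the first was not. One section can then be read as ending treatment while the other permits it to go on.

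The permitted restart also has a fault of its own. The reduction is measured from the original dose, not the current one, so a patient who has already been reduced would restart on the dose that preceded the second DLT.

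What is at stake is mainly safety, since the rule governs re-exposure after a second DLT, and then time on drug. A site that restarts the patient under 7.6.4 could be recorded as having broken 7.6.2.

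**Working it through.** **Inputs**

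- Adult starting dose 800 mg twice daily, 1600 mg/day (Tables 2 and 3). Pediatric starting dose 520 mg/m² per dose twice daily, capped at 1600 mg/day (Table 3).
- Reduction factor 0.75, applied to the original dose (7.2, 7.6.2, 7.6.4).
- Tablet strength 200 mg (7.6.2, 7.6.4).
- No re-escalation (7.6.2, 7.6.4), so a reduced patient is still at the reduced level when a second DLT occurs.

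**Step 1. Reproduce the plan's figures.** Reduced dose = 0.75 x original dose.

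- Adult: 0.75 x 800 = 600 mg, and 600 / 200 = 3 tablets. Per day: 0.75 x 1600 = 1200 mg.
- Pediatric: 0.75 x 520 = 390 mg/m², with a cap of 0.75 x 1600 = 1200 mg/day.

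All agree with Table 3.

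**Step 2. Non-hematological DLT first, hematological DLT second.** The adult is on 600 mg twice daily.

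| Text | Outcome of the second event |
|---|---|
| 7.6.2 closing rule, read literally | Removal: a DLT has occurred again after restart, and no class is named |
| 7.6.4 trigger and restart rule | Hold; if resolved within 14 days, may restart at 0.75 x 800 = 600 mg |
| 7.6.4 closing rule | Not triggered: this is the first hematological DLT |
| Table 3 | No level below 600 mg twice daily |

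Change from current dose = 600 − 600 = 0 mg. For a child the level is again 0.75 x 520 = 390 mg/m², so the change in dose level is also zero.

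**Step 3. Narrower reading of 7.6.2.** Suppose recurrence there means the same class only. Its closing rule then does not reach this event, and 7.6.4 alone applies. The restart dose is still 600 mg, so the 0 mg reduction remains.

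**Step 4. Reverse order.** If the hematological DLT comes first, the second event is non-hematological and 7.6.2 governs; 7.6.4 is silent. Read literally, the closing rule of 7.6.2 gives removal. Read as same class only, its restart paragraph gives 600 mg again. The ambiguity lies within 7.6.2, not between the two sections.

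**Step 5. Scale, by assumption only.** The documents give no joint rate. Section 1.4.1 reports treatment-related grade 3 or worse thrombocytopenia in 3% and neutropenia in 3% of 99 lymphoma patients. Assume a hematological DLT rate of at most 3% + 3% = 6%, a non-hematological DLT rate of 5% to 20%, and independence. Expected subjects with both, in either order:

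- of 29: 29 x 0.06 x 0.05 = 0.09, to 29 x 0.06 x 0.20 = 0.35
- of 50, the enrollment ceiling: 50 x 0.06 x 0.05 = 0.15, to 50 x 0.06 x 0.20 = 0.60

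The population differs, and positive dependence between the two classes would raise these figures. They show scale and are not an estimate.

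**The case against.** The strongest reply is that 7.6.2 should be read within its own heading. It opens with non-hematological DLT as defined in 7.6.1, so the later unqualified term may be shorthand, and recurrence ordinarily means the same problem coming back. On that reading the sections are parallel and the mixed case is simply not addressed. This is a fair reading, and it removes the direct conflict. It does not remove the 0 mg reduction.

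A second reply is that 7.6.4 only permits restart and does not say its closing rule is the sole ground for removal, so removing the patient would comply with both sections. That also stands. A reader might infer that the two sections cannot both be obeyed, and the text does not go that far. But a site that uses the permission in 7.6.4 would still breach 7.6.2 read literally, and the protocol does not say which text prevails.

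Third, there are safeguards. The trial is at a single institution, suspected DLTs go to the project management office and the principal investigator within 24 hours (7.4), and the investigator may stop drug for any adverse event (8.2). These make uneven handling less likely, but they do not state the rule.

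Two further inferences should be resisted:

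- **A third outcome of 450 mg.** Taking 25% off the current dose gives 0.75 x 600 = 450 mg, but no passage supports it. Sections 7.2, 7.6.2 and 7.6.4 all measure the cut from the original dose, and Table 3 has no such level.
- **A material threat to the efficacy endpoints.** The documents do not show one. The response rate is analyzed by intention to treat (12.3), and disease assessment continues after a stop for reasons other than progression (6.4).

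**Conclusion.** The point holds within limits. A first hematological DLT in a patient already reduced for a non-hematological DLT meets two texts that point different ways if 7.6.2 is taken literally: removal, or permitted restart at 75% of the original dose. That conflict between sections depends on the literal reading and on this order of events; a reader might infer the same conflict in either order, but the documents do not support that.

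The other defect does not depend on how 7.6.2 is read: the restart that 7.6.4 calls reduced is, for an 800 mg starter, a change of 0 mg, and Table 3 offers nothing lower. It is more than missing detail, because the stated rule produces a result at odds with its own description.

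The number of subjects affected is unknown and probably small, below one expected subject under the assumptions shown. The consequence is mainly patient safety and time on drug. It should be corrected because it governs re-exposure after a second DLT and the correction is cheap.

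**What to change.** The sponsor's clinical team should reconcile the recurrence sentences of 7.6.2 and 7.6.4 with each other and with Table 3, so that all three give one consistent instruction for a DLT of the other class in a patient already at the reduced level. The revised text should state whether recurrence means the same class or any class, and should cover both orders of events. Section 7.2 repeats the reduction rule and should be checked for agreement. Which outcome applies is a clinical decision, and none is proposed here.

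The cost is a wording amendment to 7.6.2, 7.6.4 and Table 3, with the usual review board approval under 14.7. It needs no additional patients, procedures or change to the statistical design.

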### 7.6.5 Dose Modification Tables

The table in this section (Table 3) should be used for dose modifications as a result of toxicities outlined in section 7.6.

Table 3: Tazemetostat Dose Modifications for Adverse Reactions

#### Adults

Dose level	Initial Dose: 8 capsules per day
Starting Dose	Four 200-mg capsules twice daily (1600 mg/day)
Dose Reduction (by 25%)	Three 200-mg capsules twice daily (1200 mg/day)

#### Children

Dose level	Initial Dose: 8 capsules per day
Starting Dose	520 mg/m  /dose orally twice daily (up to 1600 mg/day)
Dose Reduction (by 25%)	390 mg/m  /dose orally twice daily (up to 1200 mg/day)

## 8. TREATMENT DISCONTINUATION

### 8.1 Screen Failures

Subjects who sign informed consent, but do not meet eligibility criteria, or withdraw prior to eligibility being verified, and undergo at least some of the screening procedures will be considered screening failures. Subjects who sign informed consent and are verified as eligible, but do not proceed to formal registration will be considered "unregistered." A record of screen failures and unregistered subjects will be maintained by the study site.

### 8.2 Criteria For Study Treatment Discontinuation

Subjects who discontinue participation in the clinical study on their own or subjects who are withdrawn by the investigator, for reasons other than completion of treatment, disease progression or toxicity, will be defined as premature withdrawals.

A subject will be discontinued from protocol therapy under the following circumstances:

- Any adverse event which, in the Investigator's opinion, requires termination of the study medication.
- Disease progression, unless at the discretion of the principal investigator (in collaboration with any co-sponsors or collaborators) continued treatment with study drug is appropriate.
- The subject becomes pregnant. Pregnancy will be reported along the same timelines as a serious adverse event.
- The subject uses illicit drugs or other substances, or takes part in activities that may, in the opinion of the Investigator, have a reasonable chance of contributing to toxicity or otherwise interfering with results.
- The development of a second malignancy that requires treatment, which would interfere with this study.
- The subject is lost to follow-up.
- Development of an intercurrent illness or situation which would, in the judgment of the investigator, affect assessments of clinical status and study endpoints to a significant degree.
- If subject desires to discontinue.

The Investigator will make every reasonable effort to keep each subject in the study unless it is in the subject's best interests to discontinue participation. If a subject is removed from the study or declines further participation, all EOT evaluations should be performed if the subject is willing and able to be assessed. A description of the reason(s) for withdrawal from the study must be recorded on the case report form (CRF). The Investigator should also ensure that all subjects are followed up for survival status after the Final Visit.

Relevant visit data should be entered on the CRF and any unused study medication will be accounted for and returned for all subjects participating in the study, even for a brief period of time. Subjects who discontinue following entry will have relevant information completed and recorded on the CRF. All subjects who discontinue because of adverse events or clinically significant laboratory abnormalities should be followed up until they recover or stabilize, and the subsequent outcome will be recorded. If any subject should experience a serious adverse event during the trial or within 30 days of stopping study treatment, the Investigator will inform the UF Health Data Integrity and Safety Committee.

### 8.3 Replacement of Subjects

Subjects may be replaced if they are not screen failures, have not completed at least 75% of intended doses in the first cycle, or are not discontinued for disease progression, toxicity, or any of the reasons listed in section 8.2.

Subjects who receive at least 75% of the intended doses in their first cycle will be evaluable for clinical response. Additionally, subjects who receive any dose will be evaluable for toxicity.

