##### 4.1 Number of Subjects

Up to 50 people will be enrolled in this study to achieve 29 evaluable subjects.

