### 5. REGISTRATION PROCEDURES

All consented subjects must be entered into the University of Florida's Clinical Trial Management System (OnCore) prior to assignment of a subject identification number. The study team must submit the completed study specific eligibility checklist, supporting source documentation and a copy of the signed informed consent document(s) to the UFHCC Project Management Office (PMO; [[contact]](mailto:[contact])) or their assigned Project Manager. Upon receipt of a completed eligibility packet, the designated Project Manager will review the source to verify eligibility and assign a subject number. No subject may be enrolled until his/her eligibility packet is complete and eligibility is verified by PMO. If eligibility cannot be confirmed, the project manager will query the site for clarification or additional documents as needed. Subjects failing to meet all study eligibility requirements will not be able to participate in the trial.

All eligible and enrolled subjects will receive a unique subject number. This number will be used to identify the subject throughout the study. Subjects withdrawn from the study will retain their subject number.

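### The replacement sentence in section 8.3 fails on either reading: with *or* any enrolled subject is replaceable, and with *and* most ordinary early leavers are neither evaluable nor replaceable

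*Combined protocol and SAP*

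**What the plan says.** Section 8.3 holds the only replacement rule. Its first sentence begins "Subjects may be replaced if they are not screen failures, have not completed at least 75% of intended doses in the first cycle, or". The third condition then follows, namely that they "are not discontinued for disease progression, toxicity, or any of the reasons listed in section 8.2". The second paragraph of 8.3 defines who counts for response: "Subjects who receive at least 75% of the intended doses in their first cycle will be evaluable for clinical response".

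Four other places bear on how the rule works.

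- Section 8.1 limits screen failures to "Subjects who sign informed consent, but do not meet eligibility criteria, or withdraw prior to eligibility being verified" and who had some screening done. Section 5 adds: "No subject may be enrolled until his/her eligibility packet is complete and eligibility is verified by PMO".
- Section 8.2 lists reasons for stopping protocol therapy. Besides adverse events and progression, it includes pregnancy, substance use, second malignancy, intercurrent illness, "The subject is lost to follow-up" and "If subject desires to discontinue".
- Section 4.1 sets the accrual target: "Up to 50 people will be enrolled in this study to achieve 29 evaluable subjects". Section 3.1 agrees.
- Section 12.3 analyses ORR by intent to treat, over all study patients. Sections 12.2 and 12.7 apply the boundaries to 9 and then 29 subjects.

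**The concern.** A replacement rule for a two-stage design has to do two things. It should admit subjects who could not be assessed for reasons unrelated to outcome, and it should keep out treatment failures. The 8.3 sentence joins three negative conditions with *or*, so it does not keep out failures. Changing *or* to *and* does not rescue it, because the third condition then excludes nearly every way of leaving.

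The trial is open-label and single-arm, and Appendix C derives best response from investigator assessments. In that setting, who is replaced should not depend on judgement exercised after an outcome is known. The boundaries of 2 in 9 and 10 in 29 keep their stated error rates only if replacement is unrelated to response and if it is clear which subjects make up the 9 and the 29.

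**Working it through.** **1. The plan's own figures.** Inputs from 12.2: null ORR 0.21, alternative 0.45, stop at 2 or fewer of 9, reject at 10 or more of 29.

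P(reject) = sum over x = 3 to 9 of P(X1 = x) × P(X2 ≥ 10 − x), with X1 ~ Bin(9, p) and X2 ~ Bin(20, p).

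At p = 0.21 the terms are:
- x = 3: 0.1891 × 0.1071 = 0.0203
- x = 4: 0.0754 × 0.2297 = 0.0173
- x = 5: 0.0200 × 0.4142 = 0.0083
- x = 6: 0.00355 × 0.6310 = 0.0022
- x = 7 to 9 together: 0.0004

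The sum is 0.0485. The same formula at p = 0.45 gives 0.804. The stated 5% and 80% are reproduced.

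**2. The logic of 8.3.** For an enrolled subject let A = not a screen failure, B = under 75% of cycle-1 doses, C = not stopped for progression, toxicity or an 8.2 reason. By 8.1 and section 5, A is always true after enrollment.

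| Under 75% (B) | No 8.2 reason (C) | Evaluable | Replaceable, *or* | Replaceable, *and* |
|---|---|---|---|---|
| no | no | yes | yes | no |
| no | yes | yes | yes | no |
| yes | no | no | yes | no |
| yes | yes | no | yes | yes |

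Under *or* all four rows are replaceable, including both evaluable ones. Under *and* only the last row is.

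**3. Example records.** Cycle 1 has 28 × 2 = 56 intended doses, and 75% of 56 is 42.

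- Fully dosed, progression at the first scan: evaluable, yet replaceable under *or*.
- Half the doses, stopped for drug toxicity: replaceable under *or*, although the sentence names toxicity as a bar.
- Withdraws on day 5, at most 10 of 56 doses (18%): not evaluable, and not replaceable under *and*.
- Still on drug after a dose hold, under 42 doses: replaceable under *and*, although treatment continues.
- Dies on day 12, at most 24 of 56 doses (43%): unclear under *and*. Section 8.2 does not name death, but the case might be classed as an adverse event, progression or intercurrent illness.

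**4. Consequence if non-responders are replaced.** True ORR is 0.21. Each non-responder is replaced with probability f, and accrual continues until 29 are retained or 50 are enrolled. The values of f are assumptions, since the documents give none. Results are by simulation.

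- *Dropped:* 2/9 and 10/29 are applied to retained subjects.
- *Kept:* everyone enrolled stays in the denominator, as 12.3 suggests. Stage 1 uses the first 9 enrolled, and success is an observed ORR of at least 10/29. Both choices are assumptions. With 30 enrolled, for example, 30 × 10/29 = 10.3, so 11 responses are needed.

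| f | Type I error, dropped | Type I error, kept |
|---|---|---|
| 5% | about 6% | about 3.6% |
| 10% | about 8% | about 3.0% |
| 20% | about 12% | about 2.5% |
| 30% | about 20% | about 2.1% |

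**5. Consequence if early leavers are not replaced.** Suppose a fraction d leaves in cycle 1 and counts as non-response among the 29. The effective ORR is 0.45 × (1 − d), put into the formula of step 1.

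- d = 10%: 29 × 0.9 = 26.1 evaluable, ORR 0.405, power 0.68.
- d = 20%: 29 × 0.8 = 23.2 evaluable, ORR 0.36, power 0.52.

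**The case against.** The best defence is that the aim is evident: replace under-dosed subjects, keep treatment failures. The second paragraph of 8.3 already makes a fully dosed subject with progression evaluable, so replacing that subject serves no stated purpose. A literal *or* also makes the second and third conditions redundant for enrolled subjects, which suggests a drafting slip that staff would not apply. This stands as far as intent goes. A reader might infer that the plan means to swap out known non-responders, and nothing in the documents supports that. But the defence needs the *and* reading, and that reading fails at the 8.2 reference.

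The second defence is intent to treat. Section 8.3 does not say that a replaced subject leaves the analysis, and 12.3 divides by all study patients. This also stands in part: it reverses the direction of the type I error effect, as step 4 shows. It leaves open how a 10-of-29 boundary applies when more than 29 are enrolled.

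A reader might also conclude that 29 evaluable subjects cannot be obtained on either reading. That goes too far. Under *or* the number can be reached, but the choice of the 29 is discretionary. Under *and*, sections 3.1 and 4.1 separately allow up to 50 enrolled without referring to 8.3, so the trouble is a conflict between provisions. For the same reason, the 50 − 29 = 21 extra places cannot be said to hang on 8.3 alone.

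**Conclusion.** The 8.3 sentence is wrong as written and should be amended. Under *or* it does not confine replacement to non-evaluable subjects. Under *and* it blocks ordinary cycle-1 withdrawals, who are usually non-evaluable as well, and leaves early death unclear.

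The logical fault follows from the text and needs no assumption. The numerical consequence does. It is tempting to say that the rule inflates type I error, but the documents support that only if replaced non-responders are removed from the analysis, and section 12.3 points the other way. Depending on that choice, type I error at the assumed replacement fractions of 5 to 30% runs from about 6% up to 20%, or from about 3.6% down to 2.1%, against 4.85% by design. The power loss in step 5 assumes that early leavers are not replaced and count as non-responders.

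**What to change.** Replace the first sentence of 8.3 with:

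> An enrolled subject may be replaced only if he or she received less than 75% of the intended cycle-1 doses AND left protocol therapy for a reason other than disease progression, death, or toxicity/adverse event.

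Then:

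- Delete the cross-reference to 8.2 from the sentence.
- State that a subject still on protocol therapy is not replaced.
- State that replacement is decided and logged before any post-baseline tumor assessment is read. This is workable: cycle-1 dosing is known by day 28, and the first scheduled imaging falls after two cycles (day 56, plus or minus 7 days).
- Amend the second paragraph of 8.3 so that subjects who stop early for progression, death or toxicity count as evaluable non-responders whatever their cycle-1 dosing. Without this they would be neither replaceable nor evaluable.
- Align 12.3 and 12.7 so that the 9 and the 29 to which the boundaries apply are this same set.

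The cost is a short amendment to both paragraphs of 8.3 and to two statistical sections. Treatment, eligibility and sample size do not change. The small downside is that early toxicity and death cases count as non-responders, which may slightly lower the observed ORR.
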